3.2.1.1 Primary efficacy analysis

First component of the co-primary endpoint

The first component of the co-primary endpoint is the percentage of subjects with sufficiently avid lesion(s) to be identified as a sstr2 positive lesion, i.e. the sstr2 positive prevalence in this study population. Avid is defined by the blinded readers at one of the timepoints as an easily identifiable lesion radiologically, where there has been clear focal uptake of ⁶⁸Ga-OPS202.

This will be a simple percentage calculation:

$$\begin{aligned} & \text{Percentage of subjects with avid lesion identified as sstr2 positive lesion} \\ &= \frac{\text{Number of subjects in sstr2 positive population}}{\text{Number of subjects in } ^{68}\text{Ga} - \text{OPS202 screened population}} \end{aligned}$$

A listing with the subjects in sstr2 positive population and the subjects in the ⁶⁸Ga-OPS202 screened population will be provided in order to allow computing this percentage.

Second component of the co-primary endpoint

The second component of the co-primary endpoint is based on both image quality and lesion count using the sstr2 positive evaluable population.

The selection of the optimal PET acquisition time will be done by choosing the timepoint with superior images based on overall image quality and observed higher number of lesions detected.

The number of lesions detected by ⁶⁸Ga-OPS202 in the primary breast lesions will be reported at each of the three PET acquisition timepoints (0.5, 1 and 2 hours).

Individual values of number of lesions detected by ⁶⁸Ga-OPS202 in the primary breast lesions (result from both readers as well as final result) will be listed by subject and by PET acquisition timepoint.

Image quality

After blinded reading, the readers will compare the three scans (the three acquisitions of ⁶⁸Ga-OPS202) contemporaneously for each subject and note which image(s), if any, provides superior images based on overall image quality and lesion count.

This qualitative assessment will be performed using a quality score.

For each PET/CT assessment, each independent blinded reader will perform a direct comparison of the three ⁶⁸Ga-OPS202 scans acquired at different times (0.5, 1 and 2 hours) in the primary breast lesions. The readers will be allowed to select whether one, two or all three acquisitions are optimal, attributing a score for each assessment. The readers will be blinded to timepoint sequence.

The score for the assessment having superior images will be set to “1”, and score for the assessments not selected will be set to “0”. In case two assessments are considered optimal and of equal quality, both assessments will have a score of “1” and the third one will be set to “0”. In case of equal quality between the three scans, the three assessments will have a score of “1”. Values will be available in the database provided by ICL.

In case a timepoint has been assessed as “non-readable” for the reader, the given timepoint will not be available for comparison, and therefore will have a missing quality score for that reader. Individual values of quality score for primary breast lesions and reason for selecting scan will be listed per reader, by subject and by PET acquisition timepoint.

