2.3 Study Hypothesis

The uptake of ^{68}Ga -OPS202 does not vary according to PET acquisition time within a range of 1.5 hours in subjects with sstr2 positive newly diagnosed breast cancer, taking into account the ^{68}Ga decay.

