7.1 Eligible and Evaluable Subjects

- All subjects who receive ^{68}Ga -OPS202 are “eligible” subjects and will be included in the safety analysis.
- All eligible subjects with one or more readable ^{68}Ga -OPS202 PET and a readable ceCT scan will be included in the first component of the co-primary endpoint analysis to determine sstr2 positive prevalence.
- The following describes those subjects that are eligible and “evaluable” for the second component of the co-primary endpoint to assess the optimum timing of the PET scan following infusion of ^{68}Ga OPS202:
 - A readable ceCT scan
 - At least two ^{68}Ga -OPS202 PET scans that are readable (three images are to be acquired but 2 of these, MUST be readable by the central readers; if only two PET scans are acquired BOTH must be readable) with at least one avid lesion identified by central readers.

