11.4.4 Efficacy Evaluation

As indicated in Section 7, the first component of the co-primary endpoint is the percentage of subjects with sufficiently avid lesion(s) to be identified as a sstr2 positive lesion. This will be a simple percentage calculation (number of subjects in sstr2 positive population / number of subjects in ⁶⁸Ga-OPS202 screened population). The second component of the co-primary efficacy variable is the differences in the number of lesions detected by ⁶⁸Ga-OPS202 between the three PET acquisition timepoints (0.5, 1 and 2 hours) in the primary breast lesions. The second component of the co-primary efficacy variable will be summarised by each of the three PET acquisition timepoints (0.5, 1 and 2 hours). The results could identify that one, two or all three timepoints have equal validity for future studies in this population.

As indicated in Section 7, the secondary efficacy variables are the variables measured at Visit 2 after the i.v. administration of the IIP, listed below:

Key Secondary Endpoint:

- Differences in the number of lesions detected by ⁶⁸Ga-OPS202 between the three PET acquisition timepoints (0.5, 1 and 2 hours) and reader interpretation of optimal image(s) in nodular and metastatic lesions. Significant uptake of ⁶⁸Ga-OPS202 for the evaluation of a lesion is an avid lesion defined by the blinded readers at one of the acquisition timepoints as an easily identifiable lesion radiologically, where there has been clear focal uptake of ⁶⁸Ga-OPS202 and 1.5-fold or greater uptake than in the non-tumoural liver and lung parenchyma.
- The SUV_{mean} and SUV_{max} in the primary lesion between each of the three timepoints, measured in the most avid lesions (using the ⁶⁸Ga-OPS202 scans). This is assessed by

the tumour-to-background ratio in the primary tumour and each of the major anatomic sites (liver, lymph nodes, bone, lungs and brain); the background consists of non-tumoural liver parenchyma or aortic blood where sufficient liver is not available. Identification of lesions to be used will be made by one of the two primary readers.

Other Secondary Endpoints:

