1.3.4 Planned sample size

It is anticipated that a total of 54 subjects will be enrolled in the study for ⁶⁸Ga-OPS202 screening, to obtain around 16 sstr2 positive BC evaluable subjects. Considering the estimated prevalence of sstr2 overexpression in breast cancer, the overall number of subjects to be administered ⁶⁸Ga-OPS202 in the study will be over 50. However, when the ICL identifies 16 sstr2 positive evaluable subjects, with a minimum of two subjects with advanced disease, the study will be complete.

This estimation of 16 sstr2 positive BC evaluable subjects is considered appropriate for a descriptive analysis and it is not based on a formal statistical sample size calculation. In the event that a subject misses an imaging exam and/or measurement relevant to the primary and key secondary endpoints, an additional subject will be recruited to ensure an adequate sample size in the sstr2 positive BC evaluable set.

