3.1.1 Primary efficacy endpoints

The co-primary efficacy endpoints are:

- (a) Percentage of subjects with sufficiently avid lesion(s) to be identified as a sstr2 positive lesion. (Avid is defined by the blinded readers at one of the acquisition timepoints as an easily identifiable lesion radiologically, where there has been clear focal uptake of ^{68}Ga -OPS202 and 1.5-fold or greater uptake than the non-tumoural liver and lung parenchyma).

- (b) Differences in the number of lesions detected by ^{68}Ga -OPS202 between the three PET acquisition timepoints (0.5, 1 and 2 hours), and reader interpretation of optimal image(s) in the primary breast lesions. The optimum image acquisition time could be one, two or all three acquisitions timepoints i.e. no noticeable difference between 0.5, 1 and 2 hours post infusion.

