3.1.5 Significance testing and estimation

The statistical analysis of efficacy and safety is only descriptive, therefore no formal statistical significance testing will be performed.

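### The second co-primary endpoint is a difference between imaging times, but the choice of optimum rests on no paired difference, interval or common set of women

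*SAP*

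**What the plan says.** SAP 3.1.1 defines the second co-primary endpoint as differences in lesion number between the three acquisition times, plus the readers' view of the optimal image, in the primary breast lesions. SAP 3.2.1.1 bases the selection on image quality and lesion count together, "choosing the timepoint with superior images based on overall image quality and observed higher number of lesions detected". Counts are reported at each timepoint and listed by subject for both readers and the final result. Each reader also compares the three scans side by side within a subject, blinded to time, and scores each scan 0 or 1. One, two or all three scans may score 1.

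SAP 3.1.1 describes the case where all three are optimal as "no noticeable difference between 0.5, 1 and 2 hours post infusion". Protocol 11.4.4 goes further: "The results could identify that one, two or all three timepoints have equal validity for future studies in this population". The study hypothesis in Protocol 2.3 is that uptake "does not vary according to PET acquisition time within a range of 1.5 hours". No margin is attached to any of these statements.

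On who contributes, Protocol 7.1 says "three images are to be acquired but 2 of these, MUST be readable by the central readers", and SAP 2.1.3 repeats this and adds that an avid lesion must be seen on at least two timepoints. Missing efficacy data are not imputed (SAP 3.2.3.1). An unreadable scan has a missing quality score for that reader, not a zero.

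On size and inference, SAP 1.3.4 states "This estimation of 16 sstr2 positive BC evaluable subjects is considered appropriate for a descriptive analysis" and that "it is not based on a formal statistical sample size calculation". SAP 3.1.5 adds: "therefore no formal statistical significance testing will be performed". After early termination with limited data, SAP 3.2.1 and 5 remove several analyses and the efficacy summary tables, leaving listings. The selection sentence in SAP 3.2.1.1 was kept.

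**The concern.** Each woman is scanned three times, so she is her own control and the natural estimate is the within-woman difference. The plan collects the data for it but stops at counts per timepoint and a choice between them. Three things are left open.

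- How large an observed excess in lesions must be before it counts, and how precisely it is known.
- Which women are compared, when some have only two readable scans.
- What an absence of observed difference may be taken to mean.

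The conclusion is meant for use. Protocol 11.4.4 refers to future studies, SAP 3.2.1.2 extends the selection to secondary and exploratory outputs, and SAP 2.3 allows prevalence to be re-evaluated at the agreed optimum. A chance winner, or a tie read as equality, could therefore set the imaging time for later work.

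**Working it through.** **1. The plan's own figure.** The SAP expects 54 women to yield about 16 evaluable, which implies 16/54 = 29.6%. No prevalence, effect size, margin or precision target is stated, so there is no precision calculation to reproduce.

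**2. Chance in the count criterion.** From the documents: 16 evaluable women, three scans each, lesion seen on at least two timepoints (SAP 2.1.3). Assumed, not in the documents: one primary lesion per woman, all scans readable, identical detection probability p at each time, and within-subject correlation ρ from a beta-binomial model.

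Under these conditions an evaluable woman has her lesion seen on all three scans or misses exactly one, each time being equally likely. Let d be the probability that she misses one.

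- ρ = 0: d = 3(1−p)/(3−2p). For p = 0.8, 0.6/1.4 = 0.429. For p = 0.9, 0.3/1.2 = 0.250.
- ρ > 0: with s = (1−ρ)/ρ, a = ps and b = (1−p)s, d = 3b/(3b + a + 2). For p = 0.9 and ρ = 0.3, a = 2.1 and b = 0.233, so d = 0.7/4.8 = 0.146.

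The numbers of misses at the three times are multinomial with 16 trials and probability d/3 each. A timepoint has the single highest count when its number of misses is strictly the smallest. Summing the exact probabilities gives:

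| p | ρ | d | Single highest | Two tied highest | All three tied |
|---|---|---|---|---|---|
| 0.8 | 0 | 0.429 | 72% | 24% | 4% |
| 0.8 | 0.3 | 0.266 | 63% | 30% | 7% |
| 0.9 | 0 | 0.250 | 62% | 31% | 7% |
| 0.9 | 0.3 | 0.146 | 45% | 41% | 13% |
| 0.7 | 0 | 0.563 | 76% | 21% | 3% |
| 0.95 | 0.6 | 0.037 | 8% | 37% | 55% |

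The last two rows are the extremes over p from 0.7 to 0.95 and ρ from 0 to 0.6. With an illustrative 5 women, the first and fourth settings give a single highest count in 46% and 10% of studies, and a three-way tie in 12% and 46%. Fewer women therefore means fewer chance winners and more ties.

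**3. What a tie shows.** If no woman of 16 differs between two timepoints, the exact upper 95% limit (two-sided) for the true proportion who differ is 1 − 0.025^(1/16) = 20.6%. If the true proportion is 10%, no discordant woman is seen with probability 0.9^16 = 18.5%. With 5 women the limit is 1 − 0.025^(1/5) = 52.2%.

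**4. Unreadable scans, if raw totals are compared.** Let every lesion be seen on every readable scan. Two unreadable 2-hour scans give totals of 16, 16 and 14. In the 14 women readable at all three times the totals are 14, 14 and 14. If each 2-hour scan is unreadable with probability u, the 2-hour total falls below the others with probability 1 − (1−u)^16, which is 56%, 81% and 97% for u = 5%, 10% and 20%. These rates are assumptions.

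**5. Whether to require an interval that excludes zero.** If all discordant women favour one time, the exact two-sided paired p-value is 2 × 0.5^k: 0.0625 for k = 5 and 0.031 for k = 6. In the setting of step 2 a woman can miss at most one timepoint, so a winner over both others would need 6 + 6 = 12 discordant women of 16. Such a rule would hardly ever be met.

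**The case against.** A reader might infer more than the documents support, and the other side is right to resist it.

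- *The highest count alone decides.* It does not. SAP 3.2.1.1 requires superior image quality as well, and SAP 3.2.1.2 brings in secondary and exploratory outputs. Step 2 therefore measures one criterion, not the rule. However, the readers' quality choice is itself partly based on lesion count, and nothing says how to combine two unadjudicated readers or how to proceed when quality and count disagree.
- *The plan always names a winner, or automatically declares ties equal.* Neither is so. One, two or three optimal times are allowed, and equal validity is a permitted conclusion, not a compulsory one. What is missing is anything that limits when it may be drawn.
- *There is no within-subject comparison.* The readers make one, and the paired data are listed. Only the paired summary and its interval are absent.
- *Unreadable scans bias the result.* They do so only if raw totals are compared, which the SAP neither prescribes nor rules out.
- *A significance test is needed.* The study is openly descriptive, and nothing here requires a test.

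Two further objections carry weight. The study stopped early, so the final number of evaluable women may be well below 16, and the removal of summary tables was a documented decision. Also, three scans of one lesion after one injection may be highly correlated, which lowers the chance of a spurious winner. Early termination does not remove the point: the selection sentence stands, and fewer women make a tie less informative. Read design and listing templates sit in the imaging charter and SAP Appendix 2, which were not available for this review and may settle some details.

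**Conclusion.** The concern holds in a limited form. The endpoint is a difference, but the plan specifies no paired difference, no measure of precision and no common set of women, and it permits a tie to be read as equality. With 16 women and identical timepoints, the count criterion alone would show a single highest time in about 45% to 72% of studies under the main assumptions and about 8% to 76% under the wider ones. Detection, correlation and one lesion per woman are assumed, and the figures are not the error rate of the full selection rule. The 20.6% limit depends only on the planned 16 women. The effect of unreadable scans is conditional on comparing raw totals. This is a change that should be made to the analysis and its wording. It is not a reason to add hypothesis testing.

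**What to change.** In SAP 3.2.1.1, for each pair of timepoints and using only women readable at both:

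- show how many women had more, equal or fewer lesions, using the final count;
- give the paired difference in lesion count with a descriptive exact 95% interval, naming the method;
- show the 0/1 quality scores in the same way, separately for each reader.

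Label any chosen optimum as provisional and report it with these intervals. Do not require an interval to exclude zero: that would be a test by another name, and step 5 of the working shows it would be nearly unattainable. Replace the statement on equal validity in Protocol 11.4.4 with wording that the timepoints were not distinguishable in this sample, and read the corresponding sentence in SAP 3.1.1 in the same sense.

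The cost is one small table, built from data already listed, added to an SAP that otherwise plans efficacy listings only, and a more cautious conclusion.

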7 ASSESSMENT OF EFFICACY

For the primary, secondary and exploratory endpoints all the sets of images obtained at Visit 2 and one ^{18}F -FDG-PET and one ceCT scan will be sent to an ICL for quality control and management of the reads. The centralised reads will be undertaken by two independent experienced radiologists and/or nuclear medicine physicians, and a third for adjudication of discordances for most of the reads. The readers will be specifically trained for this protocol. Full details of the read design and conduct will be provided in the IRC.

For the primary endpoint analysis, the number of lesions and quality of the images will be taken into consideration by the readers. Scans will be blinded to subject identification, site and timing post injection. No adjudication will be conducted as inter-reader differences will be part of the evaluation.

The sequence of image display and recording of results will be as follows on a per subject basis:

- (1) Review of the three image sets of ^{68}Ga -OPS202 scans in randomised fashion, with CT image fusion. The ceCT images acquired will be used for co-registration. Two readers will read and a third will adjudicate any differences.
- (2) ^{18}F -FDG-PET images for standard-of-truth assessments will be reviewed by two radiologists not involved in ^{68}Ga -OPS202 PET/CT images read, and the lesions mapped to the ^{68}Ga -OPS202 read. Two readers will read and a third will adjudicate any differences.
- (3) SUV_{max} and SUV_{mean} calculations of the five most avid lesions per organ on ^{68}Ga -OPS202 PET scans (primary breast lesion, liver, lymph nodes, bone, lungs and brain) will be conducted by the ICL after identification of the lesions by one of the primary readers.
- (4) Review of the lesion-to-background ratios in each major anatomical site (primary breast lesion, liver, lymph nodes, bone, lungs and brain) based on the evaluation of up to five most avid lesions per organ will be managed by the ICL after the lesions have been identified by one of the primary readers.
- (5) For image quality, direct comparison of the three ^{68}Ga -OPS202 scans acquired at different times, will be conducted for the primary breast cancer and then for all other lesions as the final step of the blinded read. The readers will be allowed to select whether one, two or all three acquisitions are optimal. The readers will be blinded to time point sequence. No adjudication will be required.

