- (4) Review of the lesion-to-background ratios in each major anatomical site (primary breast lesion, liver, lymph nodes, bone, lungs and brain) based on the evaluation of up to five most avid lesions per organ will be managed by the ICL after the lesions have been identified by one of the primary readers.
- (5) For image quality, direct comparison of the three ^{68}Ga -OPS202 scans acquired at different times, will be conducted for the primary breast cancer and then for all other lesions as the final step of the blinded read. The readers will be allowed to select whether one, two or all three acquisitions are optimal. The readers will be blinded to time point sequence. No adjudication will be required.
- (6) The ^{68}Ga -OPS202 PET scans will be compared with the ^{18}F -FDG-PET scans (with ceCT).

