2.1 Efficacy populations

2.1.1 *⁶⁸Ga-OPS202 screened population*

The ⁶⁸Ga-OPS202 screened population includes all subjects who received the dose of study IIP with one or more readable ⁶⁸Ga-OPS202 PET and a readable ceCT scan.

The assessment of ⁶⁸Ga-OPS202 PET scan and ceCT scan readability will be based on the imaging read named “Confirmation read”, provided by ICL.

This population encompasses both subjects with sstr2 positive lesion(s) and those with sstr2 negative lesions (i.e. no avid lesion with ⁶⁸Ga-OPS202).

2.1.2 *Sstr2 positive population*

The sstr2 positive population includes all subjects who received the dose of study IIP and for whom ⁶⁸Ga-OPS202 PET/CT scan images are readable for at least one timepoint and have one avid lesion identified by central readers.

The assessment of ⁶⁸Ga-OPS202 PET scan readability and the presence of avid lesions will be based on the imaging read named “Confirmation read”, provided by ICL.

Subjects are also required to have a ¹⁸F-FDG-PET/CT scan and a readable ceCT scan.

2.1.3 *Sstr2 positive evaluable population*

The sstr2 positive evaluable population includes all subjects from the ⁶⁸Ga-OPS202 sstr2 positive population with at least two evaluable timepoints. Subject are also required to have a ¹⁸F-FDG-PET/CT scan and a readable ceCT scan.

Evaluable subjects are those with a ceCT scan, ¹⁸F-FDG-PET scan and at least two ⁶⁸Ga-OPS202 PET scans that are readable (three images are to be acquired but two of these must be readable by the central readers. If only two PET scans are acquired both must be readable) with at least one avid lesion identified on at least 2 timepoints by central readers.

The assessment of ⁶⁸Ga-OPS202 PET scan readability and the presence of avid lesions will be based on the blinded imaging read “⁶⁸Ga-OPS202 PET Independent Review” (two readers and potential adjudication), provided by ICL.

Listings of subjects regarding inclusion in each population and satisfying the population definition and associated data will be reviewed by the study team.

The reasons for subject exclusion from each of the populations will be listed and tabulated.

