3.2.1.2 Secondary efficacy analysis

All secondary and exploratory analyses will be performed using thesstr2 positive evaluable population only.

Similar to the primary endpoint, the selection of the optimal PET imaging time of ^{68}Ga -OPS202 will be based on the provided outputs for all secondary and exploratory efficacy endpoints.

Key Secondary Endpoint:

a) Absolute number of lesions detected by ^{68}Ga -OPS202 in nodular and metastatic lesions

For each PET/CT assessment, the individual number of lesions detected by ^{68}Ga -OPS202 in nodular and metastatic lesions (result from both readers as well as final result) will be listed by subject and by PET acquisition timepoint. If there is a high number of lesions (≥ 35 lesions) in any one organ, identifying and counting of the lesions is not feasible as it cannot be accurately done. The absolute number of lesions will be presented as a category “ ≥ 35 lesions” if such case occurs.

Values will be available in the database provided by ICL.

A listing of all discrepancies between both readers in the nodular and metastatic lesions will also be presented by subject and PET acquisition timepoint.

Image quality

For each PET/CT assessment, each independent blinded reader will perform a direct comparison of the three ^{68}Ga -OPS202 scans acquired at different times (0.5, 1 and 2 hours) in nodular and metastatic lesions.

Individual values of quality score for nodular and metastatic lesions and reason for selecting scan will be listed per reader, by subject and by PET acquisition timepoint

b) Lesion SUV_{max} and tumour-to-background ratio

Lesion SUV_{max}

For each PET assessment, the SUV_{max} (unit-less measure) will be measured for each lesion, up to a maximum of the five most avid lesions per organ identified by one of the primary readers.

In order to obtain a unique measure per organ, the mean of the SUV_{max} will be computed within each of the six following organs:

- Primary breast lesion
- Liver
- Lymph nodes
- Bone
- Lungs
- Brain.

Values will be available in the database provided by ICL.

Tumour-to-background ratio

For each PET assessment, the tumour-to-background ratio will also be measured for each lesion, up to a maximum of the five most avid lesions per organ, as follow:

Tumour to background ratio

$$= \frac{\textit{Lesion SUVmean}}{\textit{SUVmean of the subject's reference tissue (tumour free liver *)}}$$

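### Does coding a non-readable scan as missing, with no stated rule for combining quality scores, leave the choice of optimal imaging time open to error?

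*SAP*

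**What the plan says.** The second co-primary endpoint combines image quality and lesion count in the primary breast lesions. SAP 3.2.1.1 picks the optimal time by "choosing the timepoint with superior images based on overall image quality and observed higher number of lesions detected".

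Quality is scored per reader. A selected scan gets 1, and more than one scan may be selected. For a readable scan that is not selected, the "score for the assessments not selected will be set to" zero. If the reader calls a scan non-readable, "the given timepoint will not be available for comparison, and therefore will have a missing quality score for that reader".

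Other rules bear on this:

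- **Evaluability (SAP 2.1.3):** "three images are to be acquired but two of these must be readable by the central readers", and an avid lesion must be seen on at least two timepoints. One unreadable scan of three is therefore compatible with being evaluable.
- **Adjudication of the quality read (SAP 1.3.2.1, step 5):** "No adjudication will be required". Protocol Section 7 gives the reason for not adjudicating: "inter-reader differences will be part of the evaluation".
- **Result allowed (SAP 3.1.1):** "The optimum image acquisition time could be one, two or all three acquisitions timepoints".
- **Output:** quality scores for the primary lesion are listed per reader, subject and timepoint. SAP 3.2.1.2 does the same for the other lesions: "Individual values of quality score for nodular and metastatic lesions and reason for selecting scan will be listed per reader".
- **General conventions:** missing efficacy data are not imputed (SAP 3.2.3.1), and percentages use non-missing values (SAP 3.2.11).
- **Scope:** the analysis is descriptive, without significance tests (SAP 3.1.5). Efficacy summary tables were dropped after the decision to stop the study early (SAP 3.2.1 and Section 5).

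**The concern.** A scan that is read but not selected counts 0. A scan too poor to read counts as nothing. If the scores were turned into shares of non-missing values, which is the SAP's general percentage convention, unreadable scans would leave their timepoint's denominator and would not count directly against it.

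Failure could also depend on time. With the 68-minute half-life in Protocol 1.2, much less activity is left at 2 h than at 0.5 h. Protocol 1.4 argues for the highest injected activity range to obtain optimal images. That argument rests on lower receptor expression and says nothing about readability over time, so the link is plausible but not documented.

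At stake is a co-primary conclusion. Two people working from the same listing could name different optimal times because they used different denominators or combined the two readers differently. SAP 2.3 also allows the agreed optimum to be reused in a supportive prevalence analysis.

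**Working it through.** The documents give no unreadable rate and no formal sample-size calculation, so there is no figure of the plan's own to reproduce. The inputs from the documents are n = 16 planned evaluable subjects (SAP 1.3.4), two readers, three timepoints and the 68-minute half-life. Everything else below is assumed.

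**1. Activity left.** 2^(−t/68) gives 0.737 at 30 min, 0.542 at 60 min and 0.294 at 120 min.

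**2. When can the denominator reverse a ranking?** Let *a* and *b* be the numbers of 1s at 2 h and 1 h, with a < b. Let *k* of *N* scores be missing at 2 h only. Shares of non-missing values reverse the order when a/(N − k) > b/N, that is, when b − a < bk/N.

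| Case | Condition | Pairs that reverse |
|---|---|---|
| One reader, N = 16, k = 1 | b − a < b/16, at most 1 | none |
| One reader, N = 16, k = 2 | b − a < b/8 | 7 (a = 8 to 14, b = a + 1) |
| Readers pooled, N = 32, one scan unreadable to both, k = 2 | b − a < b/16 | 15 (a = 16 to 30, b = a + 1) |

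- One reader, k = 2: 10/14 = 71.4% v 11/16 = 68.8%, but 10/16 = 62.5% over all acquired scans.
- Pooled: 17/30 = 56.7% v 18/32 = 56.3%, but 17/32 = 53.1% over all acquired scans.

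So one unreadable scan cannot reverse a within-reader ranking, but it can if the readers are pooled. Every reversing pair in the table differs by exactly one score.

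More missing scores allow a wider gap. With 18 v 16 selections of 32 and two 2 h scans unreadable to both readers, 16/28 = 57.1% overtakes 18/32 = 56.3%.

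**3. How readers are combined.** Assume 16 subjects with four 2 h scans unreadable to both readers. Requiring either reader to select gives 1 h 10/16 = 62.5% and 2 h 9/12 = 75.0%. Requiring both gives 1 h 62.5% and 2 h 6/12 = 50.0%. The merging rule can matter as much as the denominator.

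**4. Does the missing code favour the failing timepoint?** Assume one winner per subject, equal quality, and failure only at 2 h with probability u = 0.20.

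- *Random failure.* 2 h wins (1 − u)/3 = 26.7% of all acquired scans, or 33.3% of the readable ones. Each rival wins (1 − u)/3 + u/2 = 36.7%. The missing code already leaves 2 h behind, and a 0 widens the gap.
- *Worst scans fail.* 2 h wins (1 − u³)/3 = 33.1% over all acquired scans, and 33.1/0.80 = 41.3% over non-missing values. Each rival wins 33.5%. Here the missing code flatters 2 h, and a 0 restores near-equality.
- *One readability limit for all times, 2 h truly poorer.* Simulated with normal quality, 2 h lower by 0.5 SD, scans below −1.0 unreadable, and at least two readable scans required. About 10%, 10% and 24.5% are unreadable. The 2 h share is 28% v 44% over non-missing values and 21% v 40% over all acquired scans. Either denominator puts 2 h last.

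The direction depends on why scans fail, which the documents do not tell us. These models also force one winner, whereas the plan allows one, two or three.

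**The case for a change.** The strongest case for a change is that the optimal time is a co-primary objective, and SAP 3.2.1.1 and 3.2.1.2 keep a selection of it even in the reduced, listings-only plan. With no summary specified, whoever reads the listing must combine the scores, and step 2 shows that the answer can turn on how. The percentage convention in SAP 3.2.11 does not settle it, because no percentage of quality scores is planned and the convention does not cover merging two readers. A sentence of text would cost little.

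Part of this stands: the supplied text has no combination rule and no weighting of quality against lesion count. SAP Appendix 1 (derivations), Appendix 2 (output templates) and the Imaging Review Charter (read design) are cited but were not supplied, so it cannot be said that no rule exists.

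The stronger remedy, scoring non-readable scans 0, does not stand as an improvement. It merges scans that were compared and not chosen with scans that were never compared. It departs from the no-imputation rule. Under random failure it adds to the penalty on the failing timepoint. Limiting it to image-related failures needs a recorded reason for each non-readable scan, which the documents do not show is collected. It would still leave two unpooled readers and no weighting against lesion count, so the optimum would remain a judgement.

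**Conclusion.** No change is needed. This is missing detail that an analyst can fill sensibly from what the plan already provides, and following the SAP as written gives no wrong result.

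- Both readers' scores are listed separately with missing values visible, so anyone can see the number selected and the number readable at each timepoint and compute either share.
- Leaving the two readers unmerged is deliberate, since their disagreement is part of the evaluation.
- Reversals arise only in near-ties: one score apart in the basic cases, two of 32 in the wider example. The plan lets such timepoints share the optimum, and lesion count enters as well.
- Missing is a coherent code for a scan that could not be compared. The alternative code helps if the worst scans fail, hurts if failure is random, and leaves the ranking unchanged under a common readability limit.

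The possible effect is small. The output is descriptive, untested and, after early termination, confined to listings on limited data. The calculations rest on assumed failure rates, assumed scores and the planned 16 subjects. If the documents not supplied contain a combination rule, even the gap in detail disappears.
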